# 6.3 Exploratory Endpoints

1. To correlate T-cell changes and PDL1 expression with patients outcome. Only patients who have been administered at least one dose of investigational drug and undergone surgery will be evaluable for this endpoint.

	RANO Crite	eria for Respons	e 	
	CR	PR	SD	PD
T1 gadolinium enhancing disease	None	$\geq$ 50% decrease	< 50% decrease but < 25% increase	$\geq 25\%$ increase
T2/FLAIR	Stable or decrease	Stable or decrease	Stable or decrease	increase
New lesion	None	None	None	Present 
Corticosteroids	None	Stable or decrease	Stable or decrease	n/a
Clinical status	Stable or increase	Stable or increase	Stable or increase	decrease
Requirement for response	All	All	All	Any

# 6.4 Response Assessment (Modified RANO criteria)

The response to immunotherapy may differ from the typical responses observed with cytotoxic chemotherapy including the following (Wolchok et al 2009, Nishino et al 2013):

- Response to immunotherapy may be delayed
- Response to immunotherapy may occur after PD by conventional criteria
- The appearance of new lesions may not represent PD with immunotherapy
- SD while on immunotherapy may be durable and represent clinical benefit

Based on the above-described unique response to immunotherapy and based on guidelines from regulatory agencies, e.g., European Medicines Agency's "Guideline on the evaluation of anticancer medicinal products in man" (EMA/CHMP/205/95/Rev.4) for immune modulating anticancer compounds, the study use a modified RANO criteria to define PD:

Progressive disease post-baseline is defined as one or more of the following:

- New contrast-enhancing lesion outside of radiation field on decreasing, stable, or increasing doses of corticosteroids.
- Increase by > 50% (modified from >25% according to published RANO criteria) enhancement from the first post-surgical scan, or a subsequent scan with smaller tumor size, and the scan 8 weeks or later on stable or increasing doses of corticosteroids.
- Clinical deterioration not attributable to concurrent medication or comorbid conditions is sufficient to declare progression on current treatment.

Treatment with MEDI4736, Tremelimumab or both would continue between the initial assessment of progression and confirmation for progression. In addition, subjects may continue to receive MEDI4736, Tremelimumab or both beyond confirmed PD in the absence of clinically significant deterioration and if investigators consider that subjects continue to receive benefit from treatment.

As a secondary measure, for all response assessments, iRANO will be used for assessment.

RANO and iRANO criteria (iRANO= immunotherapy Response Assessment in Neuro-Oncology)						
	Response	Malignant glioma	Low-grade glioma	Brain metastasis		
1.	Complete Response	Disappearance of all enhancing disease for ≥4 weeks; no new lesions; stable or improved T2/FLAIR; no more than physiological steroids; clinically stable or improved	Disappearance of all enhancing and T2/FLAIR disease for ≥4 weeks; no new lesions; no more than physiological steroids; clinically stable or improved	Disappearance of all enhancing target and non-target lesions for ≥ 4 weeks; no new lesions; no steroids; clinically stable or improved		
2.	Partial response	≥50% decrease in the sum of biperpendicular diameters of enhancing disease for ≥4 weeks; no new lesions; stable or improved T2/FLAIR; stable or decreased steroid dose; clinically stable or improved	≥50% decrease in the sum of biperpendicular diameter of T2/FLAIR disease for ≥4 weeks; no new lesions; stable or decreased steroid dose; clinically stable or improved	$\geq$ 30% decrease in sum of longest diameters of target lesions for $\geq$ 4 weeks; no new lesions; stable or decreased steroid dose; clinically stable or improved		
3.	Stable Disease	NA	25–49% decrease in the sum of biperpendicular diameters of T2/FLAIR disease for ≥4 weeks; no new lesions; clinically stable or improved	NA		
4.	Progressive Disease	≥25% decrease in the sum of biperpendicular diameters of enhancing disease; or new lesions; or substantial worsened T2/FLAIR; or substantial clinical decline	≥25% decrease in the sum of biperpendicular diameters of T2/FLAIR disease; or new lesions; or substantial clinical decline	≥20% decrease in the sum of longest diameters of target lesions; or unequivocal progression of enhancing non-target lesions; or new lesions; or substantial clinical decline		

The iRANO criteria integrate into the existing RANO criteria for malignant glioma, low-grade glioma, and brain metastases by providing recommendations for the interpretation of progressive imaging changes.

Specifically, iRANO recommends confirmation of disease progression on follow-up imaging 3 months after initial radiographic progression if there is no new or substantially worsened neurological deficits that are not due to comorbid events or concurrent medication, and it is 6 months or less from starting immunotherapy. If follow-up imaging confirms disease progression, the date of actual progression should be back-dated to the date of initial radiographic progression. The appearance of new lesions 6 months or less from the initiation of immunotherapy alone does not define progressive disease. FLAIR=fluid attenuated inversion recovery; N/A=not applicable

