## 2.2 Secondary Objectives & Endpoints

- 2.2.1 To evaluate the safety of either Tremelimumab or MEDI4736 alone and in combination in patients with recurrent GBM. The endpoints will be the number, frequency, and severity of adverse events (as defined by the NCI Common Terminology Criteria for Adverse Events or CTCAE version 4.03).
- 2.2.2 To determine post-surgery, the time to progression(per Modified RANO criteria and iRANO criteria see below) for patients treated with either Tremelimumab or MEDI4736 alone and in combination of both, This will be defined as the number of months from the time of first dose of study treatment until progression of disease or death by any cause.
- 2.2.3 To determine post-surgery the overall survival for patients treated with Tremelimumab or MEDI4736 alone and in combination of both. This will be defined as the number of months surviving from the time of first dose of study treatment until death by any cause.
- 2.2.4 To assess post-surgery, MRI changes in patients treated with either Tremelimumab or MEDI4736 alone and in combination of both.

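### The size criterion for iRANO progression in section 6.4 is printed as a decrease in tumour size, contradicting the protocol's other two progression rules

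*Combined protocol and SAP*

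**What the plan says.** Section 2.2.2 sets the secondary objective: "To determine post-surgery, the time to progression(per Modified RANO criteria and iRANO criteria see below". Section 6.2 repeats it as an endpoint, counted from first dose to progression or death. Section 6.4 gives iRANO its role: "As a secondary measure, for all response assessments, iRANO will be used for assessment".

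The protocol states a size threshold for progression in three places:

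- **RANO criteria table, printed just above the section 6.4 heading.** Progression is an increase of at least 25% in T1 enhancing disease. Stable disease lies between a decrease of less than 50% and an increase of less than 25%.
- **Modified RANO list, section 6.4.** "Increase by > 50% (modified from >25% according to published RANO criteria) enhancement from the first post-surgical scan".
- **RANO and iRANO table, section 6.4, row 4 (Progressive Disease).** For malignant glioma: "≥25% decrease in the sum of biperpendicular diameters of enhancing disease; or new lesions; or substantial worsened T2/FLAIR; or substantial clinical decline". For low-grade glioma: "≥25% decrease in the sum of biperpendicular diameters of T2/FLAIR disease; or new lesions; or substantial clinical decline". For brain metastasis: "≥20% decrease in the sum of longest diameters of target lesions; or unequivocal progression of enhancing non-target lesions".

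Row 2 of that last table sets partial response for malignant glioma at "≥50% decrease in the sum of biperpendicular diameters of enhancing disease for ≥4 weeks", with further conditions on new lesions, T2/FLAIR, steroids and clinical status. The text below the table says that iRANO integrates into the existing RANO criteria. It then adds the iRANO rules on confirmation at 3 months, back-dating to first radiographic progression, and new lesions in the first 6 months.

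**The concern.** Row 4 is the only place where the protocol prints a size threshold under the iRANO label, and iRANO is one of two named criteria for a secondary endpoint. This is therefore operative text. All three cells of the row show the same reversal, so a fault in reading the PDF is unlikely.

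An assessor who applied the cell as printed would date progression from a scan on which the tumour had shrunk, and would not date it from a scan on which it had grown. Confirmed iRANO progression is back-dated to the first radiographic finding, so a wrong size call can carry into the event date used in the Kaplan-Meier analysis. An assessor who silently overrides the cell has no written iRANO size rule in that table to cite. Either way, the iRANO dates lack a sound documented basis.

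**Working it through.** No power, alpha or sample size figure enters this point. The check sets the printed size rules side by side.

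**Inputs.** Let c be the percentage change in enhancing disease from the reference scan.

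- iRANO table, row 4, malignant glioma, as printed: progression if c ≤ −25.
- iRANO table, row 2, malignant glioma: partial-response size rule c ≤ −50.
- RANO table: progression if c ≥ +25.
- Modified RANO list: progression if c > +50.

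**Classification by size alone**

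| c (%) | iRANO progression as printed | iRANO partial-response size rule | RANO table progression | Modified RANO progression |
|---|---|---|---|---|
| −80 | yes | yes | no | no |
| −50 | yes | yes | no | no |
| −40 | yes | no | no | no |
| −25 | yes | no | no | no |
| −10 | no | no | no | no |
| +10 | no | no | no | no |
| +25 | no | no | yes | no |
| +50 | no | no | yes | no |
| +51 | no | no | yes | yes |
| +100 | no | no | yes | yes |

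**What follows**

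1. Shrinkage of 25% or more meets the printed progression rule. In the RANO table, a 40% shrinkage falls in the size range for stable disease (less than a 50% decrease).
2. Any c ≤ −50 is also ≤ −25, so the partial-response size range lies wholly inside the printed progression range. The other conditions for partial response do not remove the overlap. Row 4 is a list joined by *or*, so a patient who meets every partial-response condition still meets its size limb.
3. No positive c satisfies c ≤ −25, so growth never meets the size limb, even when the enhancing disease doubles.
4. The other limbs of row 4 still work: new lesions, T2/FLAIR worsening and clinical decline. The new-lesion limb is limited in the first 6 months of immunotherapy, when new lesions alone do not define progression under iRANO. Death is an event in any case.

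**After correction.** With row 4 read as c ≥ +25, shrinkage is no longer progression and the overlap in point 2 disappears. On size, iRANO and modified RANO then differ only in threshold, for growth from 25% to 50%.

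The check leaves out the confirmation, back-dating, steroid and clinical rules.

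**The case against.** The strongest reply is that the protocol itself shows what was meant. The RANO table prints an increase, the modified RANO text restates published RANO in the same direction, and iRANO is said to build on RANO. Confirming and back-dating progression makes sense only if progression means worsening. The *NA* in the stable disease cell for malignant glioma leaves no gap, because the RANO table defines that category. An experienced neuro-oncology reader would probably notice the slip. All of this stands, and it makes the row a drafting error.

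A reader might infer three stronger things that the documents do not support:

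- **That a growing tumour cannot progress under iRANO.** This is true of the size limb only. The other limbs and death remain.
- **That the iRANO part of the objective cannot be answered.** The direction is recoverable, and the iRANO-specific rules on confirmation, timing and new lesions are unaffected by the reversal.
- **That recorded assessments are wrong.** Nothing in the documents shows that any call was made from this row. The accrual cap of 45 is only an upper bound on the patients concerned. Section 6.2 restricts this endpoint to patients who were dosed and had surgery.

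The reply does not make the row harmless. A recoverable intention is not a correct written definition, and each assessor is left to decide whether to follow the cell or override it.

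**Conclusion.** Wrong as written. The progression size criterion in row 4 of the iRANO table runs opposite to the protocol's two other progression rules, and it takes in the whole partial-response size range of its own table.

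The reach is limited to the iRANO version of the time-to-progression endpoint in section 2.2.2. Modified RANO, which section 6.4 uses to define progression, is untouched. So are the primary T-cell endpoint and the sample size in section 10.3.

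The classification above shows what the text says. It does not estimate bias, and the documents give no basis for one. The conclusion rests on two assumptions: that the printed word is the sponsor's own, which the three matching cells support, and that iRANO takes its direction from RANO, as section 6.4 states.

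**What to change.** Reconcile row 4 of the RANO and iRANO table with the RANO table and the modified RANO list, so that the endpoint's size criterion is an increase. In the malignant glioma cell, which is the one this trial uses, this means replacing *decrease* with *increase*. The other two cells need the same change if they are kept. Do this before iRANO progression dates are assigned or analysed, and check any iRANO calls already recorded from this row.

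The cost is a one-word correction in the cell that applies, made at the next amendment, plus a record check. No new procedures are needed.

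Deleting the columns that do not apply is optional tidying. Carrying the modified RANO reference scan into iRANO would add a rule that the documents do not state, so it is not part of this fix. The correction concerns the endpoint definition only and proposes no rule for treatment decisions.

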# 7.0 ADVERSE EVENTS

This study will be conducted in compliance with the Data Safety Monitoring Plan (DSMP) of the Robert H. Lurie Comprehensive Cancer Center of Northwestern University. The level of risk attributed to this study

requires high intensity monitoring, as outlined in the DSMP. In addition, the study will abide by all safety reporting regulations, as set forth in the Code of Federal Regulations.

## 7.1 Adverse Event Monitoring

Adverse event data collection and reporting, which are required as part of every clinical trial, are done to ensure the safety of subjects enrolled in the studies as well as those who will enroll in future studies using similar agents. Adverse events are reported in a routine manner at scheduled times during a trial (see Section 5 for timepoints). In addition, certain adverse events must be reported in an expedited manner to allow for optimal monitoring and patient safety and care. All patients experiencing an adverse event, regardless of its relationship to study drug, will be followed until:

- the adverse event resolves or the symptoms or signs that constitute the adverse event return to baseline;
- any abnormal laboratory values have returned to baseline;
- there is a satisfactory explanation other than the study drug for the changes observed; or
- death.

# 7.2 Definitions & Descriptions

#### 7.2.1 Adverse Event

The International Conference on Harmonization (ICH) Guideline for Good Clinical Practice (GCP) E6 (R1) defines an AE as:

Any untoward medical occurrence in a patient or clinical investigation subject administered a pharmaceutical product and which does not necessarily have a causal relationship with this treatment. An AE can therefore be any unfavorable and unintended sign (including an abnormal laboratory finding), symptom, or disease temporally associated with the use of a medicinal product, whether or not considered related to the medicinal product.

An AE includes but is not limited to any clinically significant worsening of a subject's pre-existing condition. An abnormal laboratory finding (including ECG finding) that requires an action or intervention by the investigator, or a finding judged by the investigator to represent a change beyond the range of normal physiologic fluctuation, should be reported as an AE.

Adverse events may be treatment emergent (i.e., occurring after initial receipt of investigational product) or nontreatment emergent. A nontreatment-emergent AE is any new sign or symptom, disease, or other untoward medical event that begins after written informed consent has been obtained but before the subject has received investigational product.

Elective treatment or surgery or preplanned treatment or surgery (that was scheduled prior to the subject being enrolled into the study) for a documented pre-existing condition, that did not worsen from baseline, is not considered an AE (serious or nonserious). An untoward medical event occurring during the prescheduled elective procedure or routinely scheduled treatment should be recorded as an AE or SAE.

The term AE is used to include both serious and non-serious AEs.

### 7.2.2 Severity of AEs

All adverse events will be graded according to the NCI Common Terminology Criteria for Adverse Events (CTCAE) version 4.0. The CTCAE v4.03 is available at http://ctep.cancer.gov/reporting/ctc.html

If no CTCAE grading is available, the severity of an AE is graded as follows:

- Mild (grade 1): the event causes discomfort without disruption of normal daily activities.
- Moderate (grade 2): the event causes discomfort that affects normal daily activities.
- Severe (grade 3): the event makes the patient unable to perform normal daily activities or significantly affects his/her clinical status.
- Life-threatening (grade 4): the patient was at risk of death at the time of the event.
- Fatal (grade 5): the event caused death.

All deaths that occur during the study, or within the protocol-defined 90-day post-last dose of study drug safety follow-up period must be reported as follows:

• Death that is clearly the result of disease progression should be documented but should not be reported as an SAE.

Where death is not due (or not clearly due) to progression of the disease under study, the AE causing the death must be reported as a SAE within **24 hours** (see Section 7.3.3 for further details). The report should contain a comment regarding the co-involvement of progression of disease, if appropriate, and should assign main and contributory causes of death.

Deaths with an unknown cause should always be reported as a SAE. Deaths that occur following the protocol-defined 90-day post-last-dose of study drug safety follow-up period will be documented as events for survival analysis, but will not be reported as an SAE.

## 7.2.3 Serious Adverse Events (SAEs)

All SAEs, regardless of attribution, occurring from time of signed informed consent, through 90 days after the last administration of study drug, must be reported upon discovery or occurrence.

An SAE is defined in regulatory terminology as any untoward medical occurrence that:

- Results in *death*.
  - If death results from (progression of) the disease, the disease should be reported as event (SAE) itself.
- Is life-threatening.
  - The patient was at risk of death at the time of the event; it does not refer to an event that hypothetically might have caused death if it were more severe.
- Requires in-patient hospitalization or prolongation of existing hospitalization for ≥ 24 hours.
- Results in persistent or significant disability or incapacity.
- Is a congenital anomaly/birth defect in the offspring of the subject.
- Is an important medical event that may jeopardize the patient or may require medical intervention to prevent one of the outcomes listed above.

Any event that does not meet the above criteria, but that in the judgment of the investigator jeopardizes the patient, may be considered for reporting as a serious adverse event. The event may require medical or surgical intervention to prevent one of the outcomes listed in the definition of "Serious Adverse Event". For example: allergic bronchospasm requiring intensive treatment in an emergency room or at home; convulsions that may not result in hospitalization; development of drug abuse or drug dependency.

The causality of SAEs (their relationship to all study treatment/procedures) will be

assessed by the investigator(s) and communicated to AstraZeneca.

#### 7.2.4 Adverse events of special interest (AESI)

Adverse events of special interest (AESIs) are events of scientific and medical interest specific to the further understanding of the MEDI4736 and/or Tremelimumab safety profile and require close monitoring and rapid communication by the investigator to the sponsor. MEDI4736 and/or Tremelimumab AESIs may be serious or non-serious. The rapid reporting of these AESIs allows ongoing analysis of these events in order to characterize and understand them in association with the use of this investigational product.

MEDI4736, an anti-PD-L1 antibody, and Tremelimumab, an anti-CTLA-4 antibody belong to a class of anticancer therapies, called "checkpoint-inhibitors" that amplify antitumor immune responses by blocking inhibitory signaling pathway modulated by the co-inhibitory or co-stimulatory receptors, CTLA-4 and PD-1, expressed on T cells (Callahan and Wolchok, 2013). This class of drugs can have a wide spectrum of immunemediated reactions that have been considered inflammatory in nature and can affect any organs of the body. Based on this mechanism of action of MEDI4736 and related molecules Adverse events of special interest include immune-mediated reactions such as enterocolitis, dermatitis, hepatotoxicity or hepatitis, pancreatitis endocrinopathy, neuropathy and pneumonitis.

#### 7.2.4.1 Pneumonitis

Adverse events of pneumonitis are of interest for AstraZeneca/Medimmune, as pneumonitis has been reported with anti-PD-1 MAbs (Topalian et al, NEJM 2012). Initial work-up should include high-resolution CT scan, ruling out infection, and pulse oximetry. Pulmonary consultation is highly recommended. Guidelines for the management of subjects with immune-mediated events including pneumonitis are outlined in Table 1.

Immune-mediated pneumonitis is characterized by inflammation focally or diffusely affecting the lung parenchyma that may be result of off-target effects of checkpoint inhibitors against the normal lung parenchyma. (Chow, 2013) Presentations of pneumonitis range from asymptomatic lung infiltrates to a mimic of severe bacterial pneumonia. For symptomatic patients, complaints and findings may include dyspnea, cough, tachypnea, pleuritic chest pain, and hypoxia. The frequency of immune-mediated pneumonitis in clinical trials with immune checkpoint-inhibitors ranged from  $\leq 1\%$  to 4%. (Topalian et al, 2012; Brahmer et al, 2012).

Because pneumonitis can quickly escalate and become fatal, early recognition is essential. Initial workup includes chest imaging; however, pneumonitis can have highly variable appearances on chest CT scans. In patients with pulmonary metastases or cardiopulmonary comorbidities, evaluation can be particularly challenging as it can be difficult to differentiate between infection, early pulmonary edema, alveolar hemorrhage, immune-mediated pneumonitis, immune-related tumor inflammation, and tumor progression (Topalian et al, 2012). Pneumonitis has also been reported as a complication of cancer treatment associated with lung and breast cancer.

Guidelines for the management of subjects with immune-mediated events including pneumonitis are outlined in Table 1.

